8.6.1. SEE 1: ODI

The ODI efficacy objective will be tested under the following hypotheses:

$$H_0: \mu ODI_T = \mu ODI_C$$

$$H_A: \mu ODI_T \neq \mu ODI_C$$

Where μODI_T is the mean change in ODI in the Treatment group and μODI_C is the mean change in ODI in the Control group at the Primary Endpoint Assessment Visit. The hypotheses will be tested using a two-sided two-sample t-test for a difference in mean changes.

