4.6.2. ODI

Oswestry Disability Index (ODI) is a disease specific assessment of the disabling effects of back pain.⁴⁸ The ODI covers 1 item on pain and 9 items on activities of daily living (personal care, lifting, walking, sitting, standing, sleeping, sex life, social life, and traveling). ODI is reported as a score from 0 to 100%.

The relevance of changes in ODI has been explored by many authors, and discussions abound on Minimal Clinically Important Difference (MCID), Minimally Important Change (MIC) and the like. It is important to distinguish between significance of change scores for studies on *acute* low back pain where the natural history of improvement would suggest reversion to the mean, and studies on chronic low back pain where the likelihood of improvement is low. Hägg et al⁵⁹ suggested that an absolute change of 10 (in the 100 point ODI scale) is the MCID and Ostelo⁶⁰ concurs that a Minimally Important Change is 10.

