4.6.3. EQ-5D

EQ-5D is the acronym for the European Quality of Life Score on Five Dimensions. There are many instruments used for assessment of Quality of Life,⁶¹ and EQ-5D appears to be the most commonly used in studies of therapies for back pain, and is often used for cost utility assessment.⁶² The EQ-5D descriptive system comprises the following 5 dimensions: mobility, self-care, usual activities, pain/discomfort and anxiety/depression. The original EQ-5D used a 3 level reporting system (no problems, some problems, extreme problems), and more recently a five level reporting system has been developed and validated (no problems, slight problems, moderate problems, severe problems, and extreme problems), referred to as the EQ-5D-5L, which has been tested and validated.^{63,64} This Clinical Investigation uses the EQ-5D-5L, referred to in its short form as EQ-5D.

The EQ-5D is designed for use primarily as a self-reported measure (i.e.: the questionnaire is completed by the Subject alone), and therefore lends itself to clinical trials in which the outcome assessment is to be blinded. Population norms for EQ-5D for various populations have been reported, and categorized by age, gender and social class. EQ-5D is reported as an index up to 1.00 (note: EQ-5D index scores of <0 are possible in some circumstances).

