10.3. Procedures to Amend the Clinical Investigation Plan

From time to time, an Investigator or the Sponsor may propose changes to the Clinical Investigation Plan. The Sponsor shall have final authority to make such changes or not.

From time to time, the DMC may mandate or recommend changes to the Clinical Investigation Plan. From time to time, regulatory authorities may mandate or recommend changes to the Clinical Investigation Plan.

All amendments to the CIP shall be agreed upon by the Sponsor and the Investigators and be recorded with a justification for the amendments. In all cases of changes to the Clinical Investigation Plan, the local rules for approval of modifications shall be followed, including by way of example a submission to the IRB or Ethics Committee (either in full or to the Chairman), and modifications to the clinical Trial contract with the institution if applicable.

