10.7. Sponsor Responsibilities

MML US Inc. (a subsidiary of Mainstay Medical Limited, Ireland) ("Mainstay") is the Sponsor of this study, where a Sponsor is defined as an individual or organization taking the responsibility and liability for the intention or implementation of a clinical investigation.

It is the responsibility of the Sponsor to ensure proper monitoring of the study and to see that all clinical requirements are met. In addition, Sponsor representatives may participate in the conduct of the Trial to the extent described in the following section on the role of the Sponsor representatives. In this study Sponsor representatives are not blinded to the study results, particularly since Sponsor representatives may be involved in device programming. Participation in the study will be limited to Sponsor personnel who are appropriately qualified and trained such as those personnel with an engineering, technical or nursing degree or equivalent training, or significant experience within the implantable device industry. All Sponsor personnel will be trained on the appropriate clinical study regulations and guidelines for medical device trials.

It is the responsibility of the Sponsor to ensure appropriate training of all individuals involved in the clinical Trial. This includes Investigators and other health care professionals at the investigational sites, Sponsor personnel, and contractors if applicable.

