7.2. Missing Data and Sensitivity Analyses

The primary efficacy endpoint will be assessed in the ITT Cohort, consisting of all randomized Subjects not in the Surgical Roll In Cohort, with missing endpoint assessments examined in sensitivity analyses. Secondary efficacy endpoints will be assessed in the population of Subjects with complete data (baseline and at the Primary Endpoint Assessment Visit). Sensitivity analyses of the impact of missing data will include a tipping point analysis for the primary efficacy endpoint where the endpoint is computed with possible combinations of imputed success and failure for Subjects with missing primary efficacy assessment. Additionally, for the primary and secondary efficacy endpoints, a last observation carried forward analysis will be conducted.

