7.4. Pooling of Data Across Trial Sites

Poolability of data will be assessed using a Mantel-Haenszel (MH) test procedure to examine the null hypothesis of a common odds ratio of responders across sites. The data will be considered poolable if the p-value for the test is ≥ 0.15 . If the p-value is < 0.15 additional analyses will be conducted to determine whether the site differences are due to imbalances in baseline factors that have evidence ($p < 0.20$) of an association with the primary outcome. These analyses may include an analysis of covariance on the percentage of pain relief, used to define responders, with site included as a random effect and adjustments for baseline covariates found to be associated with pain relief. If poolability across sites is not demonstrated, then results for the primary endpoint may be stratified and presented by site groupings.

8. Statistical Analyses

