8.11. Subgroup Analyses and Predictors of Response

The primary efficacy endpoint will be analyzed in the subgroups defined below to demonstrate consistency of treatment effect. A logistic regression model will be used to test the interaction of randomization assignment and subgroup/covariate. Subgroups to be analyzed will include, at a minimum:

- Gender
- Age (as both a continuous variable and grouped in ranges)
- Ethnicity
- Baseline VAS
- BMI (as both a continuous variable and grouped in ranges)
- Duration of work status adversely affected by CLBP

Multivariable analysis to explore predictors of response will be conducted in the Treatment group Subjects. Univariable regression models with covariates as defined below will be analyzed to determine predictors of response. All covariates with an association with response ($p < 0.20$) will be included in a multivariable logistic regression model.

- Duration of back pain (as both a continuous variable and grouped in ranges)
- Baseline ODI (as both a continuous variable and grouped in ranges)
- Baseline EQ5D (as both a continuous variable and grouped in ranges)
- Baseline VAS (as both a continuous variable and grouped in ranges)
- Baseline opioid use
- Age
- Gender
- BMI
- Compliance with stimulation (the number of minutes that stimulation was actually delivered divided by the number of minutes that could have been delivered)

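### Change in ODI and EQ-5D is compared with an unadjusted t-test; adjusting for the baselines already collected is a cheap efficiency improvement whose gain may be nil

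*SAP*

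**What the plan says.** The test for ODI in SAP 8.6.1 is: "The hypotheses will be tested using a two-sided two-sample t-test for a difference in mean changes". SAP 8.6.2 uses the same sentence for the EQ-5D index, and Protocol 4.7.2.1 agrees for both. No covariate is named.

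Both baselines are recorded at Visit 1 (Protocol 6.1), and SAP 7.2 limits the secondary analyses to Subjects with a baseline and a visit value. Baseline ODI and EQ-5D are named as covariates in one place, SAP 8.11: "Multivariable analysis to explore predictors of response will be conducted in the Treatment group Subjects". That model has no arm comparison. Analysis of covariance is mentioned once, as an optional step in the poolability work of SAP 7.4: "These analyses may include an analysis of covariance on the percentage of pain relief". Its outcome is pain relief, not ODI or EQ-5D. SAP 7.2 adds that "for the primary and secondary efficacy endpoints, a last observation carried forward analysis will be conducted", again without a model.

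Allocation is 1:1 (SAP 5.1). The first five secondary endpoints go through Hochberg at 5% overall, and only after the primary endpoint is met (SAP 8.6). The SAP gives three accounts of the population for the secondary endpoints: Subjects with complete data (7.2), ITT with Per Protocol and Completers in addition (8.2), and Per Protocol (8.6).

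**The concern.** A t-test on change fixes the slope of follow-up on baseline at 1. If the true slope is lower, the chance difference between arms at baseline is over-corrected and adds noise to the estimated effect. ANCOVA estimates the slope and removes that noise. The precision given up would come from data already in hand.

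Protocol 2.3 singles out ODI as important among the secondary endpoints, and neither document states a power for ODI or EQ-5D. Protocol 4.13 keeps post-hoc analyses out of the PMA submission. If the arms happen to differ on baseline ODI, there would therefore be no planned adjusted comparison to submit.

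Under Hochberg more than ODI's own result can be at stake, because meeting or missing the threshold for its rank can also decide endpoints with smaller p-values.

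**Working it through.** **1. The plan's own figure.** SAP 6.1 assumes 50% against 25%, two-sided 5% and 80% power. With pooled variance under the null, n per arm = [1.96·√(2·0.375·0.625) + 0.8416·√(0.25 + 0.1875)]² / 0.25² = 57.7, so 58 per arm and 116 in total (power 80.2%). The figure reproduces. It concerns the primary endpoint and is unaffected by this point.

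**2. General result.** Let s0 and s1 be the baseline and follow-up SDs and ρ their correlation. With equal arms:

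- variance of change: s1² + s0² − 2ρ·s0·s1
- ANCOVA residual variance: s1²(1 − ρ²)
- difference: (s0 − ρ·s1)², which is never negative and is zero when the slope ρ·s1/s0 equals 1.

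Simulation with 58 per arm and 20,000 trials gave variance ratios (ANCOVA/change) of 0.915 with a common slope of 0.6, 0.933 with slopes of 1.0 and 0.2 and unequal residual SDs, and 1.005 with a slope of 1.0.

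**3. Size for ODI (assumed inputs).** The entry limits of 21-60% (Protocol 5.1) narrow the baseline. Assume a latent baseline with mean 42 and SD 14; cut to 21-60, its SD is 9.85. Let k be the follow-up SD divided by 14, so the slope is ρk. Residual variance is (14k)²(1 − ρ²), and the change score adds (1 − ρk)²·9.85².

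Example, k = 1.0 and ρ = 0.4: residual 196·0.84 = 164.6; added 0.36·97.0 = 34.9; reduction 34.9/199.6 = 17.5%.

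| Variance reduction | ρ=0.4 | 0.5 | 0.6 | 0.7 |
|---|---|---|---|---|
| k=1.0 | 17.5% | 14.2% | 11.0% | 8.0% |
| k=1.3 | 7.4% | 4.6% | 2.2% | 0.5% |
| k=1.5 | 4.0% | 1.8% | 0.3% | 0.1% |

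One degree of freedom costs about 1% of variance at 116 Subjects. A hypothetical 80% power for the t-test becomes 86.7% in the best cell and 79.7% in the worst (slope 1.05). Simulated type I error was 0.047-0.053 for both tests.

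**4. Size for EQ-5D (assumed inputs).** The reduction is v(1 − ρk)² / [v(1 − ρk)² + k²(1 − ρ²)], where v is the share of baseline variance left after selection. With v = 1 it is 15-30% at k = 1.0, 1-14% at k = 1.3 and 0.2-8% at k = 1.5. Because EQ-5D covers "mobility, self-care, usual activities, pain/discomfort and anxiety/depression", the VAS and ODI entry limits restrict it too. With v = 0.60-0.88 the ranges are 10-27%, 0.6-12% and 0.1-7%. The DASS limit is not modelled and would lower them further.

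**5. Baseline imbalance in points.** With 58 per arm, the SE of the baseline ODI difference is 9.85·√(2/58) = 1.83. A 1-SE imbalance shifts the unadjusted difference by |1 − slope|·1.83, which is 0.1 to 1.1 points over the grid; at 1.96 SE it is 0.2 to 2.2. Protocol 4.6.2 cites the view that "an absolute change of 10 (in the 100 point ODI scale) is the MCID". This shift is the same quantity as the variance gain, not a second benefit: at k = 1.0 and ρ = 0.4, 1.097²/6.88 = 17.5%, where 6.88 = 199.6·2/58 is the variance of the unadjusted difference.

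**6. Hochberg.** Thresholds from the largest p-value down are 0.05, 0.025, 0.0167, 0.0125 and 0.01.

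- ODI largest, others 0.04, 0.03, 0.02, 0.014: ODI at 0.049 rejects all five; ODI at 0.051 rejects none.
- ODI second largest, others 0.20, 0.02, 0.018, 0.015: ODI at 0.024 rejects ODI and the three smaller p-values; ODI at 0.026 rejects none.

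**The case against.** **The test is valid and the gain may be nothing.** This stands. The t-test is pre-specified, consistent between Protocol and SAP, and unbiased under randomization. No stated power is missed. Every size above rests on assumed inputs, and the upper figures need k = 1.0. A reader might infer that the planned analysis is wrong or that the trial is too small; the documents support neither.

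**The population.** This stands and limits the point. Per Protocol membership depends on events after randomization, such as delivering at least 80% of sessions (SAP 8.2). Arms there may be unequal and baseline differences systematic. With a systematic baseline difference D and slope b, the t-test targets the adjusted effect plus (b − 1)D; for illustration, D = 4 and b = 0.4 put the two targets 2.4 points apart. A reader might infer that ANCOVA is never worse, and leaves the mean-change hypotheses untouched, in whichever population is used. That holds only for Subjects as randomized with about equal arms.

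**A large p-value elsewhere.** A reader might infer that if another endpoint has p = 0.20, extra precision can help only ODI. The second Hochberg example shows otherwise.

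**Site.** Randomization is stratified by site and the proposed model omits it. So does the planned t-test, and up to 40 sites could spend up to 39 degrees of freedom on 116 Subjects. A site term is a separate choice and does not weaken the case for the baseline term.

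**SAP 7.4 could admit baseline ODI or EQ-5D as covariates.** True, but in an optional model for pain relief, so it gives no adjusted comparison of these two endpoints.

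**Conclusion.** The point holds as a low-severity, optional improvement in efficiency on two gated secondary endpoints. In the randomized population with about equal arms, ANCOVA costs almost nothing (79.7% power against 80.0% in the worst case examined) and reduces the variance by about 0-18% for ODI and 0-30% for EQ-5D, for correlations of 0.4-0.7 and SD ratios of 1.0-1.5. The algebra is certain; the size is not, because the documents give no SD or correlation. Even the largest imbalance shift, 2.2 ODI points, is well below 10 points. Neither the primary test nor the sample size is affected.

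**What to change.** In SAP 8.6.1 and 8.6.2 and in the ODI and EQ-5D paragraphs of Protocol 4.7.2.1, replace the t-test sentence with text such as:

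*The hypothesis will be tested two-sided in a linear model for the Primary Endpoint Assessment Visit value, with terms for randomized arm and the continuous baseline value, in ITT Subjects with both values. The adjusted mean difference and its 95% CI will be reported, and its p-value enters the Hochberg procedure. The unadjusted t-test on change is a sensitivity analysis.*

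In SAP 7.2, state that the last-observation-carried-forward analysis of these two endpoints uses the same model. With baseline in the model, the arm coefficient is the same for the visit value and for the change, so in Subjects as randomized the hypotheses on mean change can stay. SAP 7.2, 8.2 and 8.6 should be reconciled on the population. Where the model is also fitted in the Per Protocol population, note that adjusted and unadjusted results may estimate different quantities.

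Make and date the change before anyone who decides on the analysis has seen these endpoints by arm. The date matters because Protocol 10.7 says: "In this study Sponsor representatives are not blinded to the study results".

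Cost: wording in three SAP sections and one Protocol section, and one degree of freedom. No new data are needed and no Subjects are lost, since anyone with a change score has a baseline. The Protocol part is an amendment: "All amendments to the CIP shall be agreed upon by the Sponsor and the Investigators" (Protocol 10.3), with a recorded justification and local approval at up to 40 sites. It can travel with the next amendment.

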8.6.2. SEE 2: EQ-5D

The EQ-5D efficacy objective will be assessed under the following hypotheses:

$$H_0: \mu EQ5D_T = \mu EQ5D_C$$

$$H_A: \mu EQ5D_T \neq \mu EQ5D_C,$$

where $\mu EQ5D_T$ is the mean change in EQ-5D (index score) in the Treatment group and $\mu EQ5D_C$ is the mean change in EQ-5D in the Control group from baseline to the Primary Endpoint Assessment Visit. The hypotheses will be tested using a two-sided two-sample t-test for a difference in mean changes.

8.6.3. SEE 3: Percent Pain Relief

The secondary Percent Pain Relief efficacy objective will be tested under the following hypotheses:

$$H_0: \mu PPR_T = \mu PPR_C$$

$$H_A: \mu PPR_T \neq \mu PPR_C$$

Where μPPR_T is the mean percent pain relief in the Treatment group and μPPR_C is the mean percent pain relief in the Control group at the Primary Endpoint Assessment Visit. The hypotheses will be tested using a two-sided two-sample t-test for a difference in mean changes.

8.6.4. SEE 4: Subject Global Impression of Change

The secondary Subject Global Impression of Change efficacy objective will be tested under the following hypotheses:

$$H_0: \text{DISTRIBUTIONSGIC}_T = \text{DISTRIBUTIONSGIC}_C$$

$$H_A: \text{DISTRIBUTIONSGIC}_T \neq \text{DISTRIBUTIONSGIC}_C$$

Where $\text{DISTRIBUTIONSGIC}_T$ is the distribution of the Global Impression of Change in the Treatment group and $\text{DISTRIBUTIONSGIC}_C$ is the distribution of the Global Impression of Change in the Control group at the Primary Endpoint Assessment Visit. The hypotheses will be tested using a two-sided Mann-Whitney test.

8.6.5. SEE 5: Resolution of Low Back Pain

The secondary Resolution efficacy objective will be tested under the following hypotheses:

$$H_0: \Pi\text{RLBP}_T = \Pi\text{RLBP}_C$$

$$H_A: \Pi\text{RLBP}_T \neq \Pi\text{RLBP}_C$$

Where ΠRLBP_T is the proportion of Subjects with a VAS back pain assessment for the previous 7 days of ≤ 2.5 in the Treatment group and ΠRLBP_C is the proportion of Subjects with a VAS back pain assessment for the previous 7 days of ≤ 2.5 in the Control group at the Primary Endpoint Assessment Visit. The hypotheses will be tested using a two-sided binomial test for a difference in proportions.

8.6.6. SEE 6: Crossover Group Analysis

Changes in all primary and secondary efficacy metrics will be evaluated in the Crossover group following the Outcome Post Crossover Visit. Outcome measures will be assessed for all Crossover Subjects, and a separate analysis will be performed for all Subjects who met the inclusion criteria for low back pain at the Primary Endpoint Assessment Visit (i.e.: prior to Crossover) (prior week average Low Back Pain VAS of $\geq 6.0\text{cm}$ and $\leq 9.0\text{cm}$ (on a 10cm scale)) and inclusion criterion for ODI (Oswestry Disability Index score $\geq 21\%$ and $\leq 60\%$). The analysis will also explore correlation of outcomes to amount of stimulation delivered.

8.7. Interim Analysis

A single interim analyses of the primary efficacy endpoint will occur when at least 50% of the original planned study enrollment has completed the Primary Endpoint Assessment Visit. This analysis will be limited to results from this cohort and will be used for purposes of a potential adaptive sample size increase. The interim analysis plan has the following characteristics:

- Only a single interim analysis is planned.
- The interim analysis can lead only to an increase in the study size, not a decrease in sample size or early study termination for benefit.
- If the conditional power at the time of the interim analysis is less than 30% or greater than 90%, then there will be no change in the study size. If between 30% and 90%, the study size may be increased up to a maximum of twice its originally designed size (that is, 2 x 116) to regain the original 80% power objective.
- The interim analysis will be performed by a third-party independent statistician under the direction of the Data Monitoring Committee (DMC), and detailed interim results, other than a DMC recommendation regarding the findings, will remain blinded to the sponsor and other study participants to prevent introduction of operational bias.

- On the basis of the interim analysis, the DMC may recommend one of three actions: continue the study as is, increase the sample size, or as is always an option, potentially stopping the study for reasons of safety or futility.

At the time of an interim analysis, based on the estimated conditional power, a sample size re-estimation may be performed using the method of Cui et al.^a The results will not be used to decrease the original sample size estimate or provide a basis for early study stopping for positive efficacy results. However, if it is determined that an excessive number of additional Subjects are required, a decision to recommend stopping the study early for futility may be made.

Since there is no potential for early termination benefit, no alpha adjustment to the final p-value is required other than that associated with the use of the Cui et al procedure.

8.8. Safety Analysis

8.8.1. Primary Safety Assessment

The primary safety assessment is of serious device and/or procedure related adverse events in all Subjects in the Intent to Treat Cohort at the Primary Endpoint Assessment Visit. All reported adverse events will be documented and reported with summary statistics presented for observed rates. There are no formal, statistical hypotheses being tested in the safety assessment.

There will be a separate safety analysis of Subjects in the Surgical Roll In Cohort. If numbers permit, a Poolability analysis of the ITT and the Surgical Roll In Cohort will be conducted.

8.8.2. Supporting Safety Analysis

The PMA Submission will include 12 month safety data on all Subjects implanted with ReActiv8 including all Subjects implanted in the ReActiv8-B Trial for whom 12 month safety data are available, and other persons implanted with ReActiv8 in other clinical trials (including the ReActiv8-A PMCF study) and all post-marketing registries that are registered on www.clinicaltrials.gov. This data will be provided as a separate analysis of the safety on all implanted persons as an appendix to the ReActiv8-B trial results.

A separate safety assessment will be performed on the Surgical Roll In Cohort, including a poolability analysis.

